7.2 Secondary objective(s)

- 1. To assess the use of Victoza® for weight management.
- 2. To assess the use of Saxenda® according to the approved posology.

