7.3 Endpoints

Primary endpoint:

The following endpoints will address the primary objective (concerning Saxenda® only):

BMI and comorbidities:

- Number of patients with Body Mass Index (BMI)≥30 kg/m² (measured less than 6 months before date of first prescription).
- Number of patients with 27 kg/m² ≤BMI<30 kg/m² (measured less than 6 months before date of first prescription) and
 - ≥1 relevant comorbidity registered:
 - Dysglycaemia (T2DM or prediabetes), hypertension, dyslipidaemia, and/or obstructive sleep apnoea.
 - o No relevant comorbidities (described above) registered.
- Number of patients with BMI<27 kg/m² (measured less than 6 months before date of first prescription).
- Number of patients with BMI not measured within 6 months before date of first prescription.

 Protocol
 Date:
 23 November 2015
 Novo Nordisk

 Study ID: NN8022-4241
 Version:
 5.0

 UTN: U1111-1185-3661
 Status:
 Final

 EU PAS No.:
 CONFIDENTIAL
 Page:
 17 of 53

Stopping rule:

- Number of patients with at least 5% weight loss (measured 16-24 weeks after first prescription date) and continuing treatment.
- Number of patients with less than 5% weight loss (measured 16-24 weeks after first prescription date) and continuing treatment.
- Mean weight loss (measured 16-24 weeks after first prescription date) in patients not treated according to stopping rule.

Secondary endpoint:

The following endpoint will be used to address the first secondary objective (concerning Victoza[®] only):

- Number of patients with Victoza[®] prescriptions fulfilling at least one of the following criteria:
 - 1. Dose information of 3.0 mg per day, or
 - 2. Indication of weight management.

The following endpoints will be used to address the second secondary objective (concerning Saxenda® only):

- Adherence to dose escalation according to label:
 - o Number of patients who have reached a dose of 3.0 mg within 4-12 weeks after first prescription date.
- Concomitant medication with of other GLP-1 receptor agonists:
 - Number of Saxenda[®] patients with other GLP-1 receptor agonists prescribed during continued treatment with Saxenda[®] (continued treatment is defined as no gaps between prescriptions of more than 90 days, identified by examining repeat prescription dates).
- Duration of treatment with Saxenda®:
 - o Number of patients with a treatment duration of:

Protocol		Date:	23 November 2015	Novo Nordisk
Study ID: NN8022-4241		Version:	5.0	
UTN: U1111-1185-3661		Status:	Final	

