8.1.3 Treatment of patients

Patients will be treated with commercially available Saxenda® or Victoza® according to routine clinical practice at the discretion of the treating physician. Saxenda® and Victoza® both contain the

Protocol		Date:	23 November 2015	Novo Nordisk
Study ID: NN8022-4241		Version:	5.0	
UTN: U1111-1185-3661		Status:	Final	
FILPAS No.	CONFIDENTIAL	Page.	21 of 53	

active substance liraglutide - a long-acting GLP-1 analogue, and are both administered subcutaneously by injection. The approved posology for Saxenda[®] is a starting dose of 0.6 mg daily, which should be increased to 3.0 mg daily in increments of 0.6 mg with at least one week intervals to improve gastrointestinal tolerability. For Victoza[®], the approved posology is a starting dose of 0.6 mg daily, which should be increased to 1.2 mg after at least one week; based on glycaemic response, the daily dose can be increased from 1.2 mg to 1.8 mg after at least one week.

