8.2.6 Flowchart

The data collection period for Saxenda[®]/Victoza[®] will be the interval between the launch date of Saxenda[®] to the index date of the pilot or full study, respectively. Table 1 and Table 2 show the data to be collected respectively for Saxenda[®] and Victoza[®] patients at different time points in relation to initiation of treatment. Data collection will encompass the following treatment periods for Saxenda[®]: (1) a time frame of 6 months prior to treatment initiation, (2) treatment initiation, (3) 4-12 weeks post treatment initiation, (4) 16-24 weeks post treatment initiation, and also (5) throughout the entire treatment period. Data collection will encompass the following treatment periods for Victoza[®]: (1) treatment initiation, and (2) throughout the entire treatment period.

Protocol	UTN: U1111-1185-3661	Date:	23 November 2015	Status:	Final	Novo Nordisk
Study ID: NN8022-4241	EU PAS No.:	Version:	5.0	Page:	23 of 53	

Table 1 - Saxenda® patients¹

Weeks in relation to initiation of treatment/time of first prescription	Prior to treatment initiation	0	4 – 12 weeks	16 – 24 weeks	Throughout the treatment period ²
Visit window			+4 weeks	+4 weeks	
Demography ³		X			
Co-morbidities ⁴	X				
Body Weight		X^5		X^6	
Adult height	X				
BMI		X^5			
Brand name		X			
Indication prescribed		X			
Target dose prescribed		X			
Current dose ⁷			X	X	
Treatment start date		X			
Treatment stop date					X
Concomitant medication with GLP-1					
receptor agonists					X
(Brand name and start date)					

- 1) Inclusion criteria must be fulfilled (incl. obtained informed consent) before data extraction is performed
- 2) Censoring at 24 months after launch
- 3) Sex, age
- 4) Diagnosis of or treatment of pre-diabetes, type 2 diabetes mellitus (T2DM), hypertension, dyslipidaemia and/or obstructive sleep apnoea.
- 5) Latest recording within 6 months before first prescription of Saxenda®
- 6) If not available the earliest subsequent body weight and date of measurement should be recorded
- 7) If treatment discontinuation occurs prior to/between the specified time points, the dose of Saxenda® at time of treatment discontinuation should be recorded.

Protocol		Date:	23 November 2015	Novo Nordisk
Study ID: NN8022-4241		Version:	5.0	
UTN: U1111-1185-3661		Status:	Final	
EU PAS No.:	CONFIDENTIAL	Page:	24 of 53	

Table 2 - Victoza® patients¹

Weeks in relation to initiation of treatment/time of first prescription	0	Throughout the treatment period ²

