8.7.1 Evaluability of patients for analysis

The full analysis set (FAS), including all recruited patients, will be analysed in the study.

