Saxenda® patients only:

- Comorbidities:
 - Dysglycaemia (T2DM or prediabetes), hypertension, dyslipidaemia, and/or obstructive sleep apnoea (number and proportion)
- Dose at 4-12 weeks and 16-24 weeks post initiation of treatment (mean, standard deviation)
- Duration of treatment (or ongoing treatment) (mean, standard deviation, median, first and third quartiles and range; number and proportion for treatment completion: completed treatment or ongoing treatment)

Victoza® patients only:

- Increase in Victoza® dose to 3.0 mg/day (number and proportion)
- Prescription of Victoza® for weight management (number and proportion)

Prescription outside label:

Descriptive statistics for the following:

Saxenda® patients:

- BMI<27 kg/m² (number and proportion)
- 27 kg/m²≤BMI<30 kg/m² and no relevant comorbidities registered (dysglycaemia (T2DM or prediabetes), hypertension, dyslipidaemia, and/or obstructive sleep apnoea) (number and proportion)
- BMI not measured within 6 months before date of first prescription (number and proportion)
- Non-adherence to dose escalation according to label (i.e., 3.0 mg not reached within 4-12 weeks after date of first prescription) (number and proportion)
- Non-adherence to stopping rule (i.e., less than 5% weight loss after 16-24 weeks on Saxenda® 3.0 mg and still on continued treatment) (number and proportion)

Protocol		Date:	23 November 2015	Novo Nordisk
Study ID: NN8022-4241		Version:	5.0	
UTN: U1111-1185-3661		Status:	Final	
EU PAS No.:	CONFIDENTIAL	Page:	31 of 53	

• Concomitant medication with other GLP-1 receptor agonists (brand name) (number and proportion)

Victoza® patients:

- Dose information of 3.0 mg per day (number and proportion)
- Prescribed indication of weight management (number and proportion)

All analyses will be performed using SAS 9.2 (or higher) statistical software (SAS Institute Inc., Cary, North Carolina, USA). Programs, logs, and output will be reviewed for accuracy according to relevant standard operating procedures.

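### Saxenda dose at 16-24 weeks is planned only as a mean and SD that, on a plain reading, pools current doses with last doses of stopped patients, so the number on 3.0 mg is not reported

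*Protocol*

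**What the plan says.** The second secondary objective in section 7.2 is "To assess the use of Saxenda® according to the approved posology". In section 7.3 its only dose endpoint is "Number of patients who have reached a dose of 3.0 mg within 4-12 weeks after first prescription date". Concomitant use of other GLP-1 receptor agonists and treatment duration are the other posology endpoints.

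Section 8.7.2, in the list for Saxenda patients only, gives the dose actually taken as "Dose at 4-12 weeks and 16-24 weeks post initiation of treatment (mean, standard deviation"). The dose at treatment initiation is handled differently in the same section: target dose is tabulated by category, with number and proportion.

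Table 1 in section 8.2.6 has a current-dose row for both windows, with footnote 7: "If treatment discontinuation occurs prior to/between the specified time points, the dose of Saxenda® at time of treatment discontinuation should be recorded". Section 8.7.1 states the analysis set: "The full analysis set (FAS), including all recruited patients, will be analysed in the study".

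Two counts in section 8.7.2 involve the 3.0 mg dose in Saxenda patients. One concerns escalation: "3.0 mg not reached within 4-12 weeks after date of first prescription) (number and proportion"). The other is non-adherence to the stopping rule: "less than 5% weight loss after 16-24 weeks on Saxenda® 3.0 mg and still on continued treatment) (number and proportion"). Section 8.1.3 describes a dose "which should be increased to 3.0 mg daily in increments of 0.6 mg with at least one week intervals".

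**The concern.** Two features of the planned summary work together.

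- **Type of variable.** Dose takes a few fixed levels. A mean and SD of such a variable do not show how many patients are at any one level.
- **Who is in it.** A patient who stopped in week 2 still has a value in the current-dose row for 16-24 weeks. With all recruited patients analysed and no on-treatment restriction stated, that value goes into the mean although the patient is taking nothing.

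Early stopping and continued treatment below 3.0 mg are different utilisation findings, and the planned figure does not separate them. A patient who reached 3.0 mg by week 12 and was later on a lower dose meets the escalation endpoint, and no other planned count shows the later dose. The number on 3.0 mg at 16-24 weeks would also help in reading the stopping-rule count, which section 8.7.2 ties to that dose.

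**Working it through.** **Plan figures.** Section 8.2.1 plans 75 Saxenda patients per country in the full study: 2 × 75 = 150. The total reproduces: 2 × (25 + 25) + 2 × (75 + 75) = 400. The protocol gives no expected dose distribution or stopping rate, so every dose count below is an assumption.

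**Step 1: what is counted at each window.**

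| Window | Mean and SD of dose | Count tied to 3.0 mg |
|---|---|---|
| 4-12 weeks | Yes | Reached (7.3) and not reached (8.7.2) |
| 16-24 weeks | Yes | Only patients with under 5% loss, on 3.0 mg and continuing (8.7.2) |

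The 16-24 week count is a subset of those on 3.0 mg. It leaves out everyone on 3.0 mg who lost 5% or more.

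**Step 2: do mean and SD fix the share at 3.0 mg?** Take levels 0.6, 1.2, 1.8, 2.4 and 3.0 mg and an assumed mean of 2.4 mg.

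- From the mean alone, the share at 3.0 mg can be 0% (all at 2.4 mg) or as high as 75% (0.75 × 3.0 + 0.25 × 0.6 = 2.40).
- With an SD of 0.6 mg as well, the range is 25% to 50%. The upper end is half at 3.0 and half at 1.8 mg. The lower end is 1/4 at 3.0, 2/3 at 2.4 and 1/12 at 0.6 mg: mean 0.75 + 1.60 + 0.05 = 2.40, variance (1/4) × 0.36 + (1/12) × 3.24 = 0.36.
- With an SD of 0.8 mg, the range is 44% to 63%.

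**Step 3: does the summary separate current from last doses?** Assume 150 recorded doses, 105 at 3.0 mg and 45 at 1.8 mg.

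- Mean = (105 × 3.0 + 45 × 1.8) / 150 = 396 / 150 = 2.64 mg.
- SD = 1.2 × √(0.7 × 0.3 × 150/149) = 0.55 mg.

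These two values do not depend on who is still on drug:

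| Case | On 3.0 mg, of 150 | On 3.0 mg, of those on treatment |
|---|---|---|
| Nobody has stopped | 105 (70%) | 105/150 = 70% |
| 45 of the 105 stopped at 3.0 mg | 60 (40%) | 60/105 = 57% |
| The 45 at 1.8 mg have stopped | 105 (70%) | 105/105 = 100% |

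The Wilson 95% intervals are 62.2-76.8% for 105/150 and 32.5-48.0% for 60/150. They do not overlap, so a direct count in a sample of this size would tell the first two cases apart.

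**Step 4: direction of the pooling effect.** Assume on-treatment patients average 2.7 mg and 20% have stopped. With last doses of 1.2 mg the pooled mean is 0.8 × 2.7 + 0.2 × 1.2 = 2.40 mg. With last doses of 3.0 mg it is 0.8 × 2.7 + 0.2 × 3.0 = 2.76 mg. The pooled mean can lie on either side of the on-treatment mean.

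**The case against.** The strongest reply is that this is table-shell detail. Section 8.7.2 presents its list as a brief account and leaves full analyses and templates to an SAP that is not at hand. That would answer a silence, but section 8.7.2 is not silent: it names the statistic for this variable, and in the same list it uses categories for target dose and both continuous and categorical summaries for treatment duration.

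A second reply is that footnote 7 governs recording, not analysis, and that a dose at 16-24 weeks could mean dose among those still treated. This stands in part. A reader might take the protocol to say that stopped patients are in the mean. It does not say so; that follows from footnote 7 read with the all-patients analysis set.

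Third, the planned SD carries information. It does: everyone on 2.4 mg gives an SD of 0, whereas 60% on 3.0 mg with 40% stopped at an average of 1.5 mg has the same mean of 2.40 mg but an SD of at least 1.5 × √(0.6 × 0.4) = 0.73 mg. The case in step 3 survives because the recorded doses are identical. For the same reason, adding the median and quartiles that section 8.7 uses for continuous characteristics would not resolve it.

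Fourth, discontinuation is reported elsewhere, through treatment duration and completed versus ongoing treatment. That is correct, but those summaries are not crossed with dose at 16-24 weeks.

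**Conclusion.** The point holds and is minor. As planned, the study does not report how many patients are on 3.0 mg at 16-24 weeks, although use according to the approved posology is a stated objective. In the assumed example, one reported mean and SD fits 40% or 70% of 150 patients on 3.0 mg. The conclusion rests on reading footnote 7 together with the all-patients analysis set; the size rests on assumed counts.

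Some stronger readings are not supported:

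- A reader might infer that the study cannot say how many patients are on 3.0 mg. Dose and treatment start and end dates are collected, so the count can be made, and 4-12 weeks is already covered by counts.
- A reader might infer that the mean is the only planned result on dose after escalation. The stopping-rule count also involves 3.0 mg, though only for a subset.
- A reader might infer that a patient who later moves to a lower dose is wrongly counted as following posology overall. The endpoint in section 7.3 is labelled as dose escalation, and such a patient did escalate.
- A reader might infer that pooling lowers the mean. Step 4 shows that the direction is not fixed.

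No view is taken here on any dose or treatment rule.

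**What to change.** In section 8.7.2, add to the dose line at 16-24 weeks, and at 4-12 weeks for consistency:

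1. Number and proportion at each recorded dose level, plus not recorded, among patients on treatment at that time, with treatment status derived from the collected start and end dates.
2. A separate row for patients who discontinued earlier, with their last dose tabulated there and kept out of the current-dose summary.
3. The number on 3.0 mg at 16-24 weeks, as a descriptive result under the posology objective.

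The mean and SD may stay if their denominator is stated as patients on treatment. The cost is a wording change and one larger table, in which some cells will be small, particularly by country with 75 Saxenda patients each. No new data, patients or visits are needed.

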EU PAS No.:	CONFIDENTIAL	Page:	18 of 53	

• 0-6, 7-12, 13-18, or 19-24 months, or ongoing (current patients), with continued treatment defined as no gaps between prescriptions of more than 90 days, identified by examining repeat prescription dates.

8 Research methods

In this document physician refers to the individual overall responsible for the conduct of the non-interventional study at a study site.

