8.1 Study design

8.1.1 Type of study

This DUS is a non-interventional, multi-centre Post Authorisation Safety Study (PASS) to investigate the use of Saxenda[®] and Victoza[®] in clinical practice in patients who have initiated treatment in the Saxenda[®] postmarketing period. The DUS involves retrospective review of patients' medical records in two selected European Union (EU) countries 24 months after launch of Saxenda[®] in each of the countries. Physician sampling will be built using several tools, including intelligence databases, e.g., IMS LifeLinkTM, in order to obtain a representative sample of Saxenda[®]/Victoza[®] prescriptions according to physician specialty and geography. This data source will be complementary to the full study and will be obtained on a quarterly basis, during the study period. It will provide, on a national level for the two targeted countries, the distribution of sites and prescribers' specialty. It will not identify individual prescribers, but rather guide the site selection for the study performed by Therefore, IMS LifeLinkTM will be used a priori to refine the sampling strategy (using regional and specialty distribution of prescribers), and a posteriori to assess the representativeness of prescribers and patients, for both the pilot and full study.

A case report form (CRF), including all the desired data elements, will be available to the selected sites; one CRF is to be completed per patient prescribed Saxenda® or Victoza®. The CRF may be completed by a trained healthcare professional at the site, or by a trained external medical record abstractor. The data will be entered pseudonymised into the CRFs.

A pilot study, to be embedded in the full study, will be conducted 6 months after launch of Saxenda[®] in each of the two countries, i.e., prior to the full DUS. The objective of the pilot study is to evaluate the feasibility of the full DUS. The feasibility will be evaluated on three main parameters:

- 1. Possibility of identifying physicians prescribing Saxenda®/Victoza® and participating sites
- 2. Possibility of identifying patients treated with Saxenda® or Victoza®

Protocol		Date:	23 November 2015	Novo Nordisk
Study ID: NN8022-4241		Version:	5.0	
UTN: U1111-1185-3661		Status:	Final	
EU PAS No.:	CONFIDENTIAL	Page:	19 of 53	

3. Availability and quality of the variables used to determine the specified endpoints (see section 7.3)

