Based on the data obtained in the pilot study, full study refinements may be necessary before the full retrospective medical record review is implemented in the two countries.

The index date, defined as the start date of data abstraction, will be 6 months after the launch of Saxenda[®] for the pilot, and 24 months after launch for the full study (see Figure 1 for an overview of the study design). The launch date may be different in the two countries. The data will be collected only after informed consent has been obtained from the patients. All study prescribers within a country will be assigned the same index date and will not be contacted prior to it. Initiation of prescriber-specific activities for selection of patient records meeting study selection criteria will commence on or following the index date. Data on drug utilisation will be censored on the index date. This approach will ensure that study procedures do not influence prescribing practices.

 Protocol
 Date:
 23 November 2015
 Novo Nordisk

 Study ID: NN8022-4241
 Version:
 5.0

 UTN: U1111-1185-3661
 Status:
 Final

Page:

20 of 53

CONFIDENTIAL

[figure not shown]

Figure 1 - DUS overview

EU PAS No .:

Notes: The index date (start date of data abstraction) for the pilot study will be 6 months following the launch of Saxenda[®] in the participating countries; data will be collected on patients from their start date of Saxenda[®]/Victoza[®] until the index date for the pilot study. The index date for the full study will be 24 months after the launch of Saxenda[®]; data will be collected on patients from their start date of Saxenda[®]/Victoza[®] until the index date for the full study. ICF: Informed Consent Form; M: month

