- Adherence to dose escalation according to label:
 - o Number of patients who have reached a dose of 3.0 mg within 12 weeks after first prescription date
- Concomitant medication use of other GLP-1 receptor agonists:
 - o Number of Saxenda[®] patients with other GLP-1 receptor agonists prescribed during continued treatment with Saxenda[®] (continued treatment is defined as no gaps between prescriptions of more than 90 days, identified by examining repeat prescription dates)
- Duration of treatment with Saxenda[®]:

Protocol		Date:	23 November 2015	Novo Nordisk
Study ID: NN8022-4241		Version:	5.0	
UTN: U1111-1185-3661		Status:	Final	
EU PAS No.:	CONFIDENTIAL	Page:	33 of 53	

- Number of patients with a treatment duration of:
 - 0-3, 4-6 months, or ongoing (current patients), with continued treatment defined as no gaps between prescriptions of more than 90 days, identified by examining repeat prescription dates.

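### Saxenda treatment duration is right-censored at the index date, but section 8.7.2 summarises it by raw mean, median and quartiles, which understate it

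*Protocol*

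**What the plan says.** All references are to the protocol.

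- **Entry.** Section 8.1.1 studies use "in patients who have initiated treatment in the Saxenda[®] postmarketing period". Section 8.2.6 sets the data window from launch to the index date. The inclusion criteria in 8.2.2 require no minimum follow-up.
- **Cut-off.** The index date "will be 6 months after the launch of Saxenda[®] for the pilot, and 24 months after launch for the full study", counted from each country's own launch and shared by all prescribers in a country (8.1.1). "Data on drug utilisation will be censored on the index date".
- **Endpoint.** Section 7.3 counts patients by duration: "0-6, 7-12, 13-18, or 19-24 months, or ongoing (current patients"). The pilot version in 8.7.3 reads "0-3, 4-6 months, or ongoing (current patients"). Continued treatment means no gap of more than 90 days between prescriptions.
- **Summary.** Section 8.7.2 reports "Duration of treatment (or ongoing treatment) (mean, standard deviation, median, first and third quartiles and range", then "number and proportion for treatment completion: completed treatment or ongoing treatment". It names no method that allows for censoring and does not say how ongoing patients enter the mean, median and quartiles.
- **Limitations.** Section 8.9 discusses records that may be incomplete over the 24 months, but not the censoring of duration.

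**The concern.** A patient who started 23 months before the index date can show up to 23 months of use. One who started two months before it can show two at most. A raw mean or median of observed time mixes how long patients stay on the drug with how recently they started.

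There are two ways to compute the stated statistics, and both go wrong in the same direction. Entering ongoing patients at their time so far treats the cut-off as if it were a stop. Leaving them out keeps only the stops that occurred before the cut-off, which favours short durations.

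Duration of use is a named endpoint of the second secondary objective, in a study whose whole purpose is description, and 8.7.2 has results evaluated by country. Two countries with identical persistence but differently shaped uptake would show different raw medians.

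**Working it through.** The protocol states no expected duration, discontinuation rate or uptake, so there is no figure of its own to reproduce. The size below rests on assumptions.

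**Inputs from the protocol.** Window L = 24 months (8.1.1); 150 Saxenda patients in the full study, 75 per country (8.2.1).

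**Assumptions.** Exponential durations with true median 3 to 18 months. Starts spread uniformly over the 24 months, then varied.

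**Set-up.** Let T be true duration and F = 24 − month of start. Observed time is X = min(T, F), and the patient is ongoing if T > F. With λ = ln 2 / true median:

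- Share ongoing = (1 − exp(−24λ)) / (24λ).
- Raw median, ongoing included: solve exp(−λx)(1 − x/24) = 0.5.
- Raw median, completers only: median of the density proportional to λ exp(−λt)(1 − t/24) on 0 to 24.
- Raw mean, ongoing included = (1/λ)(1 − share ongoing).

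**Worked case, true median 9 months.** λ = 0.0770 and 24λ = 1.848.

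- Share ongoing = (1 − 0.1575)/1.848 = 0.456.
- At x = 5.57, exp(−0.429) × (1 − 0.232) = 0.651 × 0.768 = 0.500, so the raw median is 5.6 months, 38% below 9.
- Raw mean = 12.98 × 0.544 = 7.1 months against 12.98, 46% low.

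| True median (months) | Ongoing at index date | Raw median, ongoing included | Raw median, completers only | Bias of raw mean, ongoing included |
|---|---|---|---|---|
| 3 | 18% | 2.5 (−16%) | 2.4 (−19%) | −18% |
| 6 | 34% | 4.3 (−28%) | 3.8 (−36%) | −34% |
| 9 | 46% | 5.6 (−38%) | 4.6 (−49%) | −46% |
| 12 | 54% | 6.5 (−46%) | 5.1 (−58%) | −54% |
| 18 | 65% | 7.8 (−57%) | 5.7 (−69%) | −65% |

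**Uptake varied.** Replace (1 − x/24) by (1 − x/24)² for linearly rising uptake, or by 1 − (x/24)² for linearly falling (front-loaded) uptake.

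- Rising, true median 9: 4.1 (−54%) with ongoing included, 3.5 (−61%) in completers. At 18: 5.2 (−71%) and 4.1 (−77%).
- Front-loaded, true median 9: 7.6 (−15%) and 5.5 (−39%). At 3: 2.9 (−2%) and 2.7 (−8%).

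The same true median of 9 months therefore appears as 4.1, 5.6 or 7.6 months depending only on the shape of uptake.

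**Month bins.** Reading them as consecutive six-month intervals, with uniform starts and a true median of 6 months, as shares of all patients:

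| | 0-6 | 7-12 | 13-18 | 19-24 | Ongoing |
|---|---|---|---|---|---|
| As observed | 44% | 16% | 5% | 1% | 34% |
| If all had 24 months of follow-up | 50% | 25% | 12.5% | 6% | 6% |

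The late bins are depleted, and the ongoing share is inflated.

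**Does Kaplan-Meier work at this size?** In 2,000 simulated samples of 150 patients (exponential durations, uniform starts), true medians of 3, 6, 9, 12 and 18 months were estimated at 2.98, 6.01, 8.98, 12.03 and 18.07. At 18 the median was not reached in 14% of samples.

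**Numbers at risk, true median 9, uniform starts.**

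- 6 months: 150 × 0.630 × 0.75 ≈ 71.
- 12 months: 150 × 0.397 × 0.50 ≈ 30.
- 18 months: 150 × 0.25 × 0.25 ≈ 9, or about 5 per country. With rising uptake, 150 × 0.25 × 0.0625 ≈ 2 overall.

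**The case against.** The strongest case on the other side is that the endpoint in 7.3 is a count by duration category, not an estimate of persistence. The category list keeps ongoing patients apart, and 8.7.2 also reports completed against ongoing. The study is descriptive, and duration is not among the off-label categories that form its main analysis. Full detail is deferred to a statistical analysis plan that is not shown and could add a time-to-event analysis.

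Much of this stands. It limits the point to one secondary endpoint and clears the bins of simple understatement. It does not rescue the mean, median and quartiles, which 8.7.2 itself names and which are biased low on either treatment of ongoing patients. A descriptive purpose does not excuse a biased description.

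Three stronger readings are tempting, and the documents support none of them:

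- A reader might infer one fixed size, such as a third to a half. The result depends on unstated persistence and uptake and runs well outside that band in both directions.
- A reader might infer that the month bins also understate persistence. Censored patients are not counted there as short durations, and the ongoing share errs upward if read as 24-month persistence.
- A reader might infer that different launch dates spoil the country comparison. Each index date is set from that country's own launch, so the windows are equal; only the shape of uptake can differ.

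The small numbers at risk at 18 months are also a fair objection to asking for late or by-country estimates without a condition.

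**Conclusion.** The point holds for the raw mean, median and quartiles: staggered starts and a common index date right-censor duration, and these statistics understate it. Under exponential durations and uniform starts, with true medians of 3 to 18 months, the raw median is 16% to 57% low with ongoing patients included and 19% to 69% low in completers only. Under the other uptake shapes checked, the shortfall runs from about 2% (front-loaded, short use, ongoing included) to 77% (rising, long use, completers only). None of these sizes comes from the documents.

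For the bins the claim is weaker: late bins are depleted by unequal follow-up, and the single ongoing category mixes very different times on drug. The primary BMI and stopping-rule endpoints do not use these summaries and are untouched. The change should be made, but the study does not depend on it.

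**What to change.** In 8.7.2:

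1. Make Kaplan-Meier time to discontinuation, censored at the country index date, the summary of duration. Report the median (or that it was not reached) and the percentage still on treatment at 6 and 12 months, with 95% confidence intervals and numbers at risk. Give 18-month and by-country estimates only where numbers at risk allow.
2. State how patients whose last prescription falls within 90 days of the index date are classified. From prescription dates alone, the gap rule cannot yet tell a stop from ongoing use in them.
3. Drop the raw mean, median and quartiles as estimates of treatment duration, or label them as observed time on treatment up to the index date and say how ongoing patients enter.
4. Keep the month bins as a descriptive count, with ongoing patients split by time on drug.

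Kaplan-Meier assumes that persistence does not change with time since launch; a sentence in 8.9 should say so. The cost is wording and a little more analysis, with wider stated uncertainty. Start, end and repeat prescription dates are already collected (8.3).
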